Since men are frequently neglected in global health programs to improve maternal and child health, the BISP-CT plus LSB proposal for "couples" is an innovative strategy to test the involvement of men towards better maternal and child health. The extent of major maternal health deficits in Pakistan cannot be stressed enough; therefore, involving men is the new initiative which is being tested in this project. Previously mixed results were obtained in terms of reducing poverty and violence against women when BISP-CT & LSB were administered specifically to women only. Through the addition of men, the impact of LSB is proposed to be enhanced. Furthermore, the proposed study not only measures women empowerment alone but also couples' empowerment through the interventions mentioned above. The purpose is to improve maternal and child health by empowering women through LSB training to BISP beneficiary married couples.

Problem Statement

Women in Pakistan are deprived of basic human rights of education, health and economic independence. Women remain dependent on their husbands, financially and socially.

Studies conducted in other part of the world have supported CT and LSB to reduce poverty, depression and violence. Recently, the negative consequences of maternal depression on children have also been well documented.

Situational Analysis

The current situation of women in Pakistan due to financial dependence and poor life skills, as described above, makes the role of our research more imperative in combating this issue through innovative interventions.

More specifically, the scope of this project is to improve maternal mental health by decreasing depression, empowering women economically and psychosocially so that they can prevent their victimization from violence and improve their health and family. Since children brought up in a healthy environment will grow up to build stronger families and hence the vicious cycle of continuing violence can be interrupted and stopped.

Therefore there is a need to test the interventions related to financial enhancement with LSB training to decrease maternal morbidity (depression), domestic violence, increase women financial empowerment, maternal and child health and nutrition.

Hypothesis

Introduction of LSB to BISP-CT beneficiaries in couples will reduce domestic violence and depression in married women of reproductive age by 20% and improve women empowerment by 20%.

Aim and Objective

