The aim of this research is in line with the 2030 agenda for Sustainable Development Goals. This agenda is a plan of action to strengthen universal peace and recognizes poverty as the greatest hurdle in sustainable development. The first goal of this document is concerned with a step of reducing poverty and the second goal aims to bring the efforts for gender equality by empowering women. Through BISP-CT intervention, it is hoped that the overall economic wellbeing of the women and their families will improve and through LSB, women will become more empowered. Ultimately they will be able to compete in the world as global citizen alongside men (Agenda for Sustainable Development, 2030). This study aims to engage men in women empowerment (MEWE) through LSB and BISP-CT to improve maternal mental health in Pakistan using a randomized control trial.

Primary Objectives

To measure the impact of men engagement in LSB and CT on maternal depression, domestic violence, improved self-efficacy and women empowerment.

Secondary Objectives

To measure the impact of men engagement in LSB and CT on Household food security, Gender Attitude, Economic Solvency and Resilience.

Primary Outcomes

Reduced maternal depression, domestic violence, improved self-efficacy and women empowerment.

Secondary Outcomes

Improved household food security, gender attitude, economic solvency and resilience.

Method

Program Implementation and Approach

The proposed study areas for the Formative Phase of the project are Punjab (Rahimyar Khan), Balochistan (Lasbela), Khyber Pukhtunkhuwa (Peshawar) and Sindh (Thatta). The cRCT will be conducted in district Thatta.

Key Intervention

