In community, the participants will be provided awareness sessions on novel corona virus and measure to keep the surroundings safe and healthy. Furthermore, they will be provided PPEs (face masks and sanitizers). In order to maintain the safety and wellness of both LSB teachers and participants, social distancing and frequent hand washing will be ensured during each session. Large groups sessions will be avoided and the number of participants will be restricted between 5-6 per session. Two sessions per day will be conducted instead of one by each pair of LSB teacher, to train 10-12 participants as per the plan of delivery.

Figure 4. Schematic illustration

Process Outcome Measures

Outcome measures for men and women receiving LSB training are the same. Process indicators include number of couples trained, number of sessions attended by couples, and number of follow-up assessments completed.

Data Management

Pre-testing

The translated versions of the questionnaires will be pre-tested by being administered to approximately 10% of the sample size in a district similar to the selected district. The completed questionnaires will be sent for data entry so that the psychometric properties of the scales will be checked. Any difficulties in translation, comprehension or item performance will be resolved by team discussion after this and final changes made to the questionnaire.

Tracking Participants

The study dataset will be a closed cohort and so it is important to track participants to determine cause of any loss to follow up and also to be able to connect interviews completed at different rounds. In order to do this we will complete an enrolment form for each couple in the study. These will be completed on paper and will be stored under lock and key at Aga Khan University. Each tracking form will include a randomly generated 6 digit number which will be that couple's

research ID and initials. In electronic data the couples will only be identified by research ID and initials which cannot be electronically linked to their name.

The tracking form will include the following information:

- Allocated ID
- Name
- Union Council, Tehsil, District
- Address
- Contact numbers
- CNIC numbers of couple

Assessment Tools

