The revised conflict tactics scale consists of 20-item and is self-administered. The scale includes items regarding Negotiation (1-4), Psychological aggression (5-8), Physical assault (9-12), Sexual coercion (13-16) and Injury (17-20). The scoring criteria consists of a scale from 1-8, 1-6 indicates the frequency of conflict happened in the past year ranging from once to more than 20 times. 7 indicates conflict happened not in the past year but happened before that. If it never happened, 8 will be marked (Douglas & Straus, 2004). There are many ways to score the CTS: Respondents who reported being a victim of or perpetrating an item or items (Prevalence). The number of times an item occurred in the past year (Frequency). Classifying each case into three categories: none, minor only, or severe (severity level). Classifying each case as respondent only, partner only, or both (mutuality types). For this study, Sindhi translated version will be used after pre-testing.

Patient Health Questionnaire (PHQ-9)

The Patient Health Questionnaire (PHQ) is a self-administered instrument for common mental disorders. The PHQ-9 is the depression module, which scores each of the 9 DSM-IV criteria as "0" (not at all) to "3" (nearly every day). It is used to monitor the severity of depression and response to treatment. It can be used to make a tentative diagnosis of depression in at-risk population (Kroenke, Spitzer, & Williams, (2001). For this study, the Urdu adaptation of the PHQ-9 tool will be used (Ahmad et al., 2018). This tool has been translated into Sindhi language and will be used in this study. PHQ-9 total score for the nine items ranges from 0 to 27. Scores of 5,

10, 15, and 20 represent cut points for mild, moderate, moderately severe and severe depression, respectively.

The Resilience Scale (RS-14)

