will be compared to the planned intervention delivery schedule and deviations will be flagged and fed back to the project management team.

The research team will have responsibility for spot checks on the fidelity logs and field visits to ensure accurate, timely and smooth data collection and the LSB intervention delivery. The field coordinators will visit each intervention site independently for the monitoring of data collection and LSB intervention.

Project Management Structure and Organization

The overall responsibility for the study is on PI, component lead and co-lead and Co-PIs from the Aga Khan University School of Nursing and Midwifery, Psychiatry and Community Health Sciences department and they will have final scientific responsibility for the study including the research conduct, reporting of main outcomes, stakeholder relations and dissemination of findings. They will be supported in this role by technical advisor [name] of Texas Woman University. The project is multidisciplinary and will draw on expertise from a range of faculty members from other disciplines at Aga Khan University.

Technical and Financial Reporting

This team will report technically and financially to PI and Co-PI of Umeed-e-Nau (UeN) at COE-WCH, AKU and the funding agency.

Ethical Considerations

Ethical approval will be obtained for the present study from Ethics Review Committee (ERC) of Aga Khan University (AKU) Karachi. Permission for data collection will be taken from the concerned stakeholders. Study related material will be explained verbally and a brief description of study will also be provided in the consent form. It is also clearly explained in the consent form that there is no benefits or potential risk attached with the study. Furthermore, the members were given the right to withdraw at any stage of the study. Keeping in view the comfort level of participants the qualitative data collection (FGDs & KIIs) will be carried out in local languages. For Sindh the guides will be used in Sindhi language while for Khyber Pakhtunkhwa (KPK) the guides will be used and facilitated in Pashtu language. However, participants from Rahim Yar Khan and Labella will mainly be facilitated using Urdu version of interview guides will be used.

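### The protocol says participants are told the study carries no potential risk, which conflicts with its own COVID-19 precautions and its questions on assault and sexual coercion

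*Protocol*

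**What the plan says.** Ethical Considerations opens with approval for the whole project ("Ethical approval will be obtained for the present study from Ethics Review Committee (ERC) of Aga Khan University (AKU) Karachi") and then reports the content of consent, namely that the form explains that "there is no benefits or potential risk attached with the study". The rest of that section covers the right to withdraw, the language of the qualitative interviews, and data storage and access.

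Elsewhere the protocol says the following.

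- **Primary Outcomes:** "Reduced maternal depression, domestic violence, improved self-efficacy and women empowerment". Domestic violence is therefore a primary outcome.
- **Assessment Tools, CTS2S-20:** besides negotiation, the items cover "Psychological aggression (5-8), Physical assault (9-12), Sexual coercion (13-16) and Injury (17-20". One of the scoring options listed is "Respondents who reported being a victim of or perpetrating an item or items (Prevalence".
- **Inclusion and Exclusion Criteria, and Tracking Participants:** the unit recruited is the couple, with one enrolment form per couple.
- **Process Outcome Measures:** men and women who receive the life-skills training have the same outcome measures.
- **Safety protocols amid COVID 19:** masks, sanitizers, distancing and hand washing are provided for, and a list of facilities for screening, isolation and referral is to be obtained. In addition, "Large groups sessions will be avoided and the number of participants will be restricted between 5-6 per session".

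**The concern.** The protocol makes a positive statement about what participants are told, so this is not a matter of missing detail. It is also the only description of risk disclosure in the document. If the form matches the description, couples decide whether to join after being told there is nothing to weigh, while the same protocol plans around an infection risk and asks about violence inside the marriage. What is at stake is valid consent and participant safety.

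The setting makes the second part more than theoretical. The sample size assumes that 60% of the women are depressed at baseline. The Study Site section reports that 49% of women in Sindh, the trial province, consider a husband justified in beating his wife in at least one listed situation, and arguing with him is one of those situations.

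**Working it through.** The point does not depend on a calculation. The check sets the statement beside the sections it has to agree with, and then counts whom it reaches.

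**1. Against the COVID-19 section.** The stated purpose of the measures is to keep both teachers and participants safe. Key Intervention plans groups of 10 to 15 couples; the COVID-19 section limits sessions to 5 to 6 people and has each pair of teachers run two sessions a day instead of one. A plan that restructures delivery to reduce a risk to participants recognises that the risk exists. No inference is needed.

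**2. Against the violence measure.** Four steps lead to the conflict:
- domestic violence is a primary outcome, so the CTS2S-20 is central to the assessment;
- its items cover assault, sexual coercion and injury, and its scoring distinguishes being a victim from perpetrating;
- the husband is recruited into the same study;
- in the couples arm the measures for men and women are the same, so a husband there can be expected to know what his wife is asked.

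Distress, and consequences of disclosure within the couple, are foreseeable from these facts, although the protocol does not name them as risks.

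**3. Is the statement offset elsewhere?** The confidentiality text covers storage of data and access by study staff and regulators. Key Intervention separates husbands and wives for training sessions; nothing says that they are assessed separately. No procedure for distress or for disclosure of violence is described.

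**4. Whom it reaches.** The inputs are 282 couples per arm, three arms, two of them with life-skills training (one for couples, one for women only), and 25% attrition (Sample Size).
- Couples to be enrolled: 3 × 282 = 846.
- Women allocated to sessions: 2 × 282 = 564.
- Husbands allocated to sessions: 1 × 282 = 282.
- Women expected at end-line: 846 × (1 − 0.25) = 634.5, about 635. The protocol's own target before the attrition allowance is 675.

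So 846 is the number enrolled and exposed to the consent statement. It is not the number assessed on both occasions.

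**The case against.** **The form is not available.** The protocol's sentence is a loose paraphrase, and the actual wording may be better. This stands, and it limits the finding to the protocol's description. It does not remove the finding: if the form differs, the protocol misdescribes it and still needs correcting.

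**The sentence may concern only the formative phase.** The next sentence is in the past tense, and the rest of the paragraph is about focus groups and key informant interviews. But the sentence refers to the study without limitation and follows approval for the present study as a whole. The narrow reading would not rescue it either, because the formative interview guides also cover violence, in groups of 10 to 15 people.

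**Infection risk is already communicated.** Participants receive awareness sessions and protective items. This is fair, and it means they are not left uninformed during delivery. It does not reconcile the consent description with the safety section.

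**Stronger readings that the documents do not support.**
- A reader might infer that denying any benefit contradicts the hypothesis ("Introduction of LSB to BISP-CT beneficiaries in couples will reduce domestic violence and depression"). It does not. A hypothesis is what the trial tests, not something that can be promised to a participant, and the control arm receives only the cash transfer.
- A reader might infer that the wording will cause withdrawal or under-reporting of violence and so bias a primary outcome. Nothing in the protocol supports such an effect.
- A reader might count 846 women asked about violence at both time points. That ignores the 25% attrition allowance.

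**Conclusion.** The statement that there is no potential risk is wrong as written and should be corrected. It conflicts explicitly with the COVID-19 safety measures and, by direct inference, with questions on assault, sexual coercion and injury put to women whose husbands are recruited with them.

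It would apply to all 846 couples to be enrolled, including the 564 women and 282 husbands allocated to sessions. The documents give no event rate, so the size of any harm cannot be stated. The conclusion rests on two assumptions: that the sentence describes consent for the study as a whole, and that the protocol's account of the form is what the sponsor intends. It concerns consent and participant safety only and does not change the sample size or the analysis.

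A reader might go further and conclude that participants have in fact consented on an untrue statement. The documents do not show this, because the form itself cannot be read here.

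**What to change.** 1. Replace the no-risk statement in Ethical Considerations so that it agrees with the COVID-19 section and with Assessment Tools.
2. Check the actual consent form against the protocol, and correct the form if it says the same.
3. Name the foreseeable risks: infection at in-person sessions, distress from the violence and depression questions, and possible consequences of disclosure within the couple.
4. Add an assurance that spouses are interviewed separately and that answers are not shared between them only if the assessment procedures are written to provide it. The protocol does not contain such a procedure at present, and wording alone would create another unsupported statement.
5. Settle with the ethics committee how the risk wording is presented to each spouse, since the protocol does not say whether consent is taken individually or per couple.

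The cost is protocol and consent wording, one ethics committee submission, and possibly a few refusals. If the assurance in step 4 is wanted, the work of writing and following that procedure is an added cost.
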